9 TUMOR PROFILING AND MATCHED THERAPY RECOMMENDATION

9.1 TUMOR PROFILING

Initial profiling will be performed on the most recent bone marrow sample documenting relapsed/refractory, high risk or rare leukemia.

9.1.2 Rapid Heme Panel (RHP)

Leukemia/MDS sample will be profiled utilizing Rapid Heme Panel to determine the presence of oncogenic mutations at the Center for Advanced Molecular Diagnostics (CAMD) at the Brigham and Women's Hospital. Leukemia sample in an EDTA tube will be submitted directly to CAMD for profiling using the Rapid Heme Panel as specified in the Manual of Operations (Appendix 3).

The method of mutation analysis performed by the CAMD may change over time in order to permit analysis of a larger number of genes. In addition, potential CLIA-certified methods of mutation analysis that may be performed by CAMD in the future may include exome or whole genome sequencing.

If RHP testing fails and sequencing results from a comparable panel are available for a newly enrolled patient, these results may be used in the place of RHP results to inform a Matched Targeted Therapy recommendation. The decision to use this comparable sequencing data must be made by the overall study PI and after RHP testing has been attempted at least once.

9.1.3 Gene Fusion Analysis

Gene fusions analysis will be performed at Boston Children's Hospital, Children's Hospital of Philadelphia or in other CLIA-certified laboratories to allow for return of these results. With development and availability of other gene fusion assays the location of this assessment may change. The leukemia sample will be submitted to Dana-Farber Cancer Institute for nucleic acid extraction and will then be submitted for sequencing at Boston Children's Hospital or another CLIA certified laboratory as specified in the Manual of Operations (Appendix 3). With development and availability of other gene fusion assays the location of this assessment may change and may include other leukemia subtypes.

9.1.4 Other testing

Given the rapid development of new genomic technologies offered by CLIA-approved laboratories, additional tests may be performed as they are developed during the course of this protocol. These may include Nanostring assay for assessment of gene fusions and RNA Sequencing (RNASeq) among others.

Other leukemia profiling tests may be performed at the discretion of the Principal Investigator or as recommended by the expert panel if the clinical history or results of sequencing panel test indicate a particular test would have clinical utility. Any leukemia profiling test in which results will be returned to the primary oncologist will be performed in a CLIA- and / or CAP-certified laboratory. Examples of additional tests that may be performed and returned to the primary oncologist are as follows. If an enrolled participant has a leukemia for which there is published evidence supporting the occurrence of an oncogenic mutation in a proportion of participants with that leukemia type and the gene is not included in the sequencing panel test, then candidate gene sequencing may be performed. Confirmatory FISH (fluorescence in situ hybridization) or IHC (immunohistochemistry) may be performed to confirm findings on the RHP.

9.2 GENOMIC ANALYSES

RHP and Gene Fusion assay results will be analyzed in line with current protocol at Brigham and Women's Hospital/Boston Children's Hospital and Boston Children's Hospital or another CLIA certified laboratory where fusion testing is performed.

9.3 RECOMMENDATION FOR A MATCHED TARGETED THERAPY

9.3.1 Formulation of Recommendation

The Principal Investigator or one of the Pediatric Oncology Co-Investigators will utilize clinical data and the interpreted profiling data to create a treatment recommendation matched to the identified genomic alteration. As the basis for the recommendation, actionable alterations will be determined from analysis from RHP and fusion gene testing as well as any molecular/sequencing data obtained in a CLIA- and / or CAP-certified laboratory prior to enrollment. Considerations taken into account in determining the recommendation will include: IC₅₀ of a particular drug against the particular mutation identified; available drug formulations; prior therapies received; participant age and availability of data regarding a pediatric dose; side effect profiles; availability of phase I/II trials. The recommendation will be tiered according to the strength of evidence for the specific genomic alteration in leukemia, or cancer in general (Appendix 1). Additional tiering will be applied for drug availability (Appendix 2).

9.3.2 Review and Approval of Genomic Alteration and Matched Treatment Recommendation by Expert Panel

The recommendation will be reviewed and approved by a panel composed of experts from pediatric oncology, developmental therapeutics, and cancer biology. The Expert Panel will meet twice a month either in person or by conference call. Conference call-in information will be provided to the Expert Panel members to allow for travel, scheduling conflicts and to include members from all participating sites. Members of the panel will be available to the investigators for consultation during creation of the recommendation as needed.

9.3.3 Communication of Genomic Alteration and Matched Treatment Recommendation to Study Participants and Their Physician

For participants with AML, MDS, rare or other high-risk leukemia who have not had a relapse, the leukemia profiling results will be released at the time of profiling. The expert panel will address in their letter communicating results and recommendation clearly distinguish recommendations which could be considered to be acted on during upfront therapy (which are expected to be few) and those that could be considered to be acted on only at the time of non-response to standard therapy or disease recurrence.

The profiling results and matched therapy recommendation will be provided to the participants' treating oncologist in the form of a letter containing an assessment of the technical performance of the profiling, the interpreted RHP and gene fusion results, a list of the actionable alteration(s) identified and the matched targeted therapy for treatment consideration. The letter will clearly state that treatment based on the recommendation is experimental and is not known to be better than standard therapy.

An information technology (IT) systems may be employed to assist in the curation process and / or report generation and delivery. An IT based curation tool would assist the curator in systematically accessing publicly available databases such as COSMIC, Pubmed, 1,000 genomes, and OMIM during their review of each variant. Study data such as patient's somatic variants including allelic fraction, diagnosis, age and study ID number would need to be entered into an IT based curation tool. An IT based report generation tool would assist the molecular pathologist and pediatric oncologist(s) in generating and, once finalized, delivering the molecular pathology interpretation and clinical review. Study data including patient identifiers such as name, MRN, diagnosis, pathology case number, prior molecular alterations identified in patient's leukemia, and prior therapy would need to be entered into an IT based reporting tool. Such information technology solutions would be HIPAA-compliant and approved by the DFCI Information Services, Information Security Office and the local site IRB.

10 FUTURE EXPLORATORY TUMOR PROFILING

Future exploratory leukemia evaluation and profiling will be performed only after sufficient material has been collected for the RHP/gene fusion profiling performed for evaluation of a matched therapy recommendation and any subsequent samples have been prioritized to for pre-clinical studies.

In those cases in which sufficient tumor material is available, deep sequencing of targeted exomes known to be involved in cancer, RNA sequencing or whole exome sequencing may be performed. Whether these techniques identify potentially actionable alterations in addition to those identified with RHP and gene fusion assay will be explored.

Results from these exploratory studies will not be released to participants or physicians unless they are performed in CLIA-certified laboratories. If mutations with significant clinical implications are identified such as germline TP53 mutation associated with the Li Fraumeni Syndrome via a non-CLIA-certified test, results will be released only after confirmation of the result is confirmed in a CLIA-certified laboratory by a newly collected clinical specimen and the case has been discussed by the expert panel. At the time of releasing germline mutation results, participants will be offered appropriate genetic counseling.

Additional research studies may be performed with de-identified tumor and fluid specimens acquired under this research protocol. These additional research studies may include derivation of in vitro testing for drug sensitivity, cell lines and xenograft models.

11 SPECIMEN AND DATA MANAGEMENT, ACCESS AND OVERSIGHT

11.1 SPECIMEN TRACKING

Specimens will be obtained and delivered to the appropriate clinical research staff at DFCI as specified in the Manual of Procedures (Appendix 3). If additional samples are available, they will be sent for additional testing in the priority order as follows as outlined in the Manual of Procedures: 1. Fusion panel testing (Boston Children's Hospital or another CLIA-certified laboratory as appropriate) 2. RNA Sequencing, 3. Xenografting at each participating institution, 4) Oregon Health & Science University.

Specimens will be tracked using a participant and sample database created by the study staff using Redcap database software on servers at Boston Children's Hospital. The database will be maintained as secure behind the firewall at Boston Children's Hospital. Access to the database will be restricted to the approved listed study staff members.

For all testing performed in CLIA-certified laboratories, each specimen will be uniquely identified by at least 2 participants identifiers (such as the participant's name, date of birth) and the study participant case number and a specimen ID number.

Clinical research personnel will hand deliver specimens to the respective DFCI, BCH and BWH Departments and labs for processing as specified in the Manual of Procedures (Appendix 3).

Participant-derived materials not depleted by local testing will be banked in the BCH Biorepository. Participant-derived materials not depleted by testing at OHSU will be banked in the biorepository at OHSU under the control of this research protocol. If specifically requested, participant-derived materials (DNA) not depleted by testing may be returned to the Pathology Department from which the original sample was submitted.

11.2 DATA CONFIDENTIALITY AND SECURITY

The confidentiality of each participant record will be rigorously maintained using existing DFCI standards. HIPAA and state/federal government regulations for protecting participant privacy and security will be strictly

observed. Printing study documents will be discouraged and avoided whenever possible. If it is necessary to print source documentation, it will be maintained and protected by clinical research personnel and kept in a locked file cabinet. Electronic study data will be encrypted both at rest and during transfer using current industry-grade practices. All computers used in the study will be encrypted according to institutional policies. All of the databases used to support this project will be stored on the servers of the Dana-Farber / Harvard Cancer Center's (DF/HCC) Quality Assurance Clinical Trials Program and Dana-Farber Cancer Institute Research Computing. Investigators from collaborating sites will have the ability to access data containing identifiers from participants enrolled at their own site only with one exception as follows: study investigators participating in producing the identified matched targeted therapy report will be able to view identified laboratory reports of the patient's assigned to them for review. This will allow them to verify that the correct genes and variants are reviewed and reported for the correct patient. There will be granular user/group-based access control that restricts viewing of subject information.

No participant or subject-identifiable information will be given to third parties, including family members (except legal guardians of minors), unless that subject (or legal guardian of minors) has given written or witnessed consent to do so. The results of research studies may be published but all data will be de-identified prior to publication and individual subjects will not be identified.

If a participant contacts the study's project personnel, he or she will be informed of the status of the research without revealing specific findings.

11.3 ACCESS TO SPECIMENS AND DATA FOR RESEARCH PURPOSES

11.3.1 Access to Research Specimens

Access to research specimens or their derivative material by investigators other than those listed as Co-Investigators on the protocol will require, in all cases, approval by the Principal Investigator. The Principal Investigator will evaluate requests for access to these materials by balancing scientific merit and potential impact of the proposed study against the amount of remaining material. The specimens collected through this protocol may be shared with investigators other than those listed as Co-Investigators on the protocol through a Usage Agreement only if such investigators complete the following steps: i) obtain approval by the Principal Investigator; ii) Agree that samples will remain de-identified and that no attempt will be made to identify or contact study participants; iii) that any use of the material beyond that described in this protocol requires review and approval by the DFCI, and other applicable IRBs; and iv) that, when relevant, Material Transfer Agreements have been executed.

11.3.2 Data Safety Monitoring and Executive Committees

The activities governed by this protocol do not require oversight by a DSMC.

11.3.3 Data Access Oversight

In addition to the oversight provided by the DF/HCC IRB as described above, data access from the study database will be guided by institutional SOPs. All data access will occur through a secure access layer that authenticates the user. All access will be logged and periodically monitored following institutional SOPs. Investigators from collaborating sites will have the ability to access data containing identifiers from participants enrolled at their own site only.

11.3.4 Repository Oversight and Distribution

In some cases data and specimens may be shared with investigators other than those listed as Co-investigators on the protocol. Access to data by investigators other than those listed as Co-Investigators on the protocol will require, in all cases, approval by the Principal Investigator. The Principal

Investigator will serve as the Honest Broker of the specimens and data generated by this project. The Principal Investigator will evaluate requests for scientific merit and potential impact of the proposed study. Once reviewed and approved, the requested data and specimens may be released de-identified only if such investigators complete the following steps: i) obtain approval by the Principal Investigator; ii) agree that data will remain de-identified and that no attempt will be made to identify or contact study participants; iii) that any use of the data beyond that described in this protocol requires review and approval by the DFCI, and other applicable IRBs; and iv) that, when relevant, Material Transfer Agreements have been executed.

11.4 SPECIMEN PROPERTY RIGHTS

Specimens collected from participants registered at DFCI, BWH, or BCH are the property of those hospitals and will remain at those hospitals even if the staff members who obtained those specimens leave. Specimens submitted by outside institutions continue to be the property of that institution. Participant-derived materials not depleted by testing, including materials from non-BCH/DFCI/BWH sites, will be banked at BCH/DFCI. If requested, participant-derived materials (e.g., DNA) not depleted by testing may be returned to the Pathology Department from which the sample was submitted.

12 DATA ANALYSIS AND STATISTICAL CONSIDERATIONS

12.1 ACCRUAL

The feasibility rule described below requires at most 100 eligible Cohort 1 patients. After feasibility is established, an additional 100 Cohort 1 patients will be accrued to further describe the actionable mutations in disease type (specifically AML and ALL). Given increased access to CLIA fusion panel testing and research RNASeq, Cohort 1 accrual will be increased by 50 patients to further describe actionable mutations that can be found using fusion testing, and describe the alterations that are detected by RNASeq but may be missed in targeted panel assessment. Approximately 10-15 patients with recurrent / refractory leukemia, 5-10 patients with newly diagnosed AML (excluding APL), and 2-3 patients with rare leukemias are evaluated per year the DF/CHCC. Almost all of these patients receive ongoing care at the DF/CHCC. Because additional procedures are not required for enrollment onto the study and given our department previous success with enrolling patients on similar trials, we anticipate that the proportion of eligible subjects who consent to enrollment will be about 90% resulting in, on average, 11 eligible, enrolled subjects per year for Cohort 1 and 10 eligible patients for Cohort 2 at DF/CHCC. The collaborating sites, Columbia University Medical Center, Children's Hospital of Philadelphia, Children's Hospital at Montefiore, Johns Hopkins Children's Center, Seattle Children's Hospital, Children's Hospital Colorado, University of California, San Francisco, University of Chicago, Children's Hospital of Wisconsin, Memorial Sloan-Kettering Cancer Center, Children's Healthcare of Atlanta, and Children's Hospitals and Clinics of Minnesota anticipate a combined enrollment of at least 40 eligible patients per year for Cohort 1. If a patient on Cohort 2 develops refractory/relapsed disease, the patient will be changed to Cohort 1. Overall, the accrual rate will be approximately 50 Cohort 1 patients per year, and enrollment of 350 eligible patients can be completed in about 5 years. Patients will only be enrolled on Cohort 1 during this time, with patients already enrolled on Cohort 2 remaining in follow-up.

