7 REQUIRED DATA

7.1.1 At Study Enrollment:

- Participant identifiers including name, medical record number, date of birth, gender, race, ethnicity.
- Diagnosis, including immunophenotype, cytogenetics, FISH studies
- Date of enrolling diagnosis
- Status (recurrent or refractory leukemia)
- Prior treatment and response to treatment (especially targeted therapy)
- Any molecular/sequencing data obtained prior to enrollment
- Treating oncologist's name and contact information

7.1.2 Following matched therapy treatment recommendation:

- For all patients enrolled with recurrent, or refractory disease (Cohort 1)
 - Every four months: vital status, disease status, any anti-leukemia treatment(s) received since the last assessment
- For all patients with newly diagnosed high-risk disease without recurrence (Cohort 2):
 - Every six months: vital status, disease status, any anti-leukemia treatment(s) received since the last assessment
- For participants who received a matched therapy recommendation:
 - If the recommendation was not used, a query of the site PI will be performed to assess barriers to receiving the matched therapy recommendation (e.g., Provider did not agree with recommendation, drug not available, insurance denied coverage, drug not available in correct formulation, patient unable to tolerate, progressive disease, etc). Site PI response may involve contacting the treating oncologist or a limited chart review.
- For participants who receive treatment according to the matched therapy recommendation:
 - Data from chart review of the medical participant's records at the participating institutions and query of primary site PI will document dates of treatment initiation, best response to treatment,

date of best response, and date of progression while receiving treatment based on the matched therapy recommendation.

- Participants will be followed until death or for 5 years from the time of study enrollment.
- Required data will be collected using case report forms.

REQUIRED DATA

	ALL PATIENTS		Cohort 1: recurrent or refractory leukemia or MDS	Cohort 2: newly-diagnosed high-risk leukemia/MDS	ALL PATIENTS
	Screening	Enrollment	Every 4 Months after MTT Report	Every 6 Months after Enrollment	At Time of Disease Progression
Baseline Demographics ^A	X				
Pathology Report	X				X
Molecular/sequencing data previously obtained or obtained outside of this study		X			X
Vital Status			X	X	
Disease status:		X	X	X	X
Interval anti-leukemia treatment received			X	X	X

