Response to anti-leukemia treatment			X	X	
Interval progression or no interval progression ^B			X	X	X
Barriers to Receipt of Treatment			X		
Sample Submission		X			X ^C
Parent / Participant Survey (if consent)**		X			X

^ABaseline demographics include: Participant identifiers; Age; Sex; Race; Ethnicity; Enrolling institution; Diagnosis; Disease status (refractory; recurrent; newly-diagnosed high risk); Prior anti-leukemia/MDS treatment; Name and contact information for primary oncologist.

^BSites will be queried every 4 months for Cohort 1 and every 6 months for Cohort 2 regarding clinical status determined by physical exam, laboratory evaluation and any interval bone marrow analysis.

^CEach patient will have up to three samples profiled as part of the study. Additional samples from additional assessment of relapse/refractory disease (up to three per patient during protocol enrollment) may be submitted to inform exploratory objectives of the study. Additional bone marrow samples beyond the three total may be submitted, but limited to no more than three bone marrow samples over the course of three months

** for patients enrolled prior to June 15, 2021

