12.4 ASSESSMENT OF STUDY OBJECTIVES

12.4.1 Primary Objective

Feasibility of identifying an actionable alteration will be addressed by the feasibility definition outlined in section 12.2. The observed rate of patients with actionable alterations, out of all patients enrolled to cohort 1, will be reported with a 90% confidence interval. The rate of patients with actionable alterations in Cohort 2 will be similarly reported.

The observed rate of patients with actionable alteration for the ALL and AML subgroups in Cohort 1 will be estimated along with a 90% confidence interval. Based on previous enrollment, it is estimated that 94, 15, and 72 out of the planned 200 Cohort 1 patients will have relapsed/refractory B-ALL, T-ALL, and AML, respectively. The remaining 19 are expected to have other rare leukemias. The width of the 90% exact confidence interval will be no larger than 17.9%, and 20.5% for relapsed/refractory B-ALL and AML, respectively. The rate of actionable mutations in relapsed/refractory T-ALL and other rare leukemias will be described. Additionally, it is estimated that 67 newly diagnosed AML Cohort 2 patients will be enrolled by the time Cohort 1 completes accrual. The width of the 90% exact confidence interval will be no larger than 23.5% for newly diagnosed AML.

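### Does moving relapsed Cohort 2 patients to Cohort 1 leave the two reported actionable-alteration rates undefined?

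*Combined protocol and SAP*

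**What the plan says.** Section 4.1.2 places each patient in one of two cohorts according to diagnosis at entry. Cohort 1 is relapsed or refractory disease and Cohort 2 is newly diagnosed high-risk disease. Section 12.1 (Accrual) adds: "If a patient on Cohort 2 develops refractory/relapsed disease, the patient will be changed to Cohort 1". Cohort 2 is closed to accrual, "with patients already enrolled on Cohort 2 remaining in follow-up", and Section 7.1.2 sets the length of follow-up: "Participants will be followed until death or for 5 years from the time of study enrollment". Transfers can therefore still occur.

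Section 12.4.1 takes the primary rate "out of all patients enrolled to cohort 1", with a 90% confidence interval. For the other cohort: "The rate of patients with actionable alterations in Cohort 2 will be similarly reported". It expects 67 newly diagnosed AML patients in Cohort 2 and adds: "The width of the 90% exact confidence interval will be no larger than 23.5% for newly diagnosed AML". Neither section mentions movers.

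On samples, Section 9.1 has initial profiling done on the most recent marrow. Footnote C to the Section 7 table says that further samples from relapsed or refractory disease "may be submitted to inform exploratory objectives of the study". Footnote A lists, among the baseline items, "Disease status (refractory; recurrent; newly-diagnosed high risk". The definition of a candidate patient in Section 12.2 names no time point for the sample.

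**The concern.** The transfer sentence stands in the statistical section, between the site accrual estimates and the overall accrual rate, and nothing limits it to follow-up. Read literally, a patient who relapses becomes a Cohort 1 patient for every purpose. Three things would then be at stake.

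- Cohort 2 would lose exactly the patients who relapsed, so its rate would describe patients who have not relapsed and not newly diagnosed disease.
- Cohort 1, the population of the primary objective, could take in patients profiled only on a diagnosis sample. Section 2.2.5 itself says that mutations are gained and lost between diagnosis and relapse.
- The denominators would move, and with them the precision stated for the AML subgroups.

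Two analysts working from the same text could in principle publish different rates.

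**Working it through.** **1. The plan's own figures.** The method is the exact (Clopper-Pearson) two-sided 90% interval, with the width maximised over all possible counts.

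| Group | n | Plan | Recomputed |
|---|---|---|---|
| Cohort 1 feasibility set (half-width) | 100 | 8.6% | 17.28/2 = 8.64% |
| Cohort 1 B-ALL (width) | 94 | 17.9% | 17.84% |
| Cohort 1 AML (width) | 72 | 20.5% | 20.49% |
| Cohort 2 new AML (width) | 67 | 23.5% | 21.26% |

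The smallest count of 100 whose upper bound reaches 13% is 8 (4.04% to 13.97%), as the plan says. The 23.5% figure is a valid but loose bound. The documents do not say how it arose or whether it already allows for movers.

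**2. What the wording supports.**

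- Section 4.1.2 enrols by diagnosis. Section 7.1.2 describes Cohort 1 as those enrolled with recurrent or refractory disease. Section 12.2 speaks of 100 patients enrolled to Cohort 1, and Section 12.4.1 uses the same verb for the denominator. In Section 12.1 movers are changed, not enrolled.
- The accrual arithmetic has no movers in it. The lead centre expects 11 Cohort 1 patients a year and the collaborating sites at least 40. 11 + 40 = 51, which the plan rounds to about 50.
- The transfer has an operational use. Follow-up goes from six-monthly to four-monthly, and barriers to treatment are recorded only in the Cohort 1 column of the Section 7 table.
- Later samples are assigned to exploratory objectives by footnote C and by Exploratory Objective 4 in Section 12.3.3. No text directs them into the primary rate.

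These points lead to cohort at enrolment and the initial sample. Baseline disease status, already collected, identifies the cohort.

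**3. Size if movers were reassigned.** The documents give neither the share relapsing nor the rates, so the inputs below are assumptions.

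Shift in the Cohort 2 rate: let *f* be the share relapsing, *pR* the rate in relapsers and *pN* the rate in the others. The full rate is *f·pR* + (1−*f*)*·pN*. Without movers it is *pN*. The difference is *f*(*pN* − *pR*).

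- *pR* = 25%, *pN* = 10%: *f* = 0.1 gives −1.5 points, 0.3 gives −4.5, 0.5 gives −7.5.
- Rates reversed: +1.5, +4.5, +7.5.
- Equal rates: 0.

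Cohort 1 AML rate with *k* movers scored at relapse: (72 × 0.15 + *k·p*)/(72 + *k*).

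- *k* = 13, *p* = 0.30: (10.8 + 3.9)/85 = 17.3%.
- *k* = 27, *p* = 0.45: (10.8 + 12.15)/99 = 23.2%.
- *p* = 0.15: 15.0%, unchanged.

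**4. Precision for newly diagnosed AML if movers leave the 67.**

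| Movers | n left | Maximum width |
|---|---|---|
| 7 | 60 | 22.52% |
| 11 | 56 | 23.34% |
| 12 | 55 | 23.55% |
| 20 | 47 | 25.55% |
| 33 | 34 | 30.21% |
| 34 | 33 | 30.67% |

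The stated bound is first passed at 12 movers (12/67 = 17.9%), by 0.05 points. These are worst cases, with an observed rate near 50%. Near the plan's own 13.5% to 15%, the widths are 17.9% for 6 of 47 and 22.5% for 5 of 34, both inside 23.5%.

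**The case for a change.** The strongest case for a change is that no sentence settles the matter. The denominator phrase in Section 12.4.1 does not say what enrolment means for someone later changed to Cohort 1. Section 7.1.2 describes Cohort 2 as disease without recurrence, which treats cohort as current status. The rates are not expressly limited to the first sample, although up to three per patient may be profiled. The 8-of-100 threshold is fixed, but movers could in principle fill some of the 100 places. With an assumed 5% rate in directly enrolled patients, the chance of at least 8 is 0.128 with no movers. It rises to 0.250 with 10 movers at 15%, and to 0.480 with 10 movers at 30%.

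The silence stands as a fact. The inference from it is weaker. Section 7.1.2 concerns the follow-up schedule, which is where the transfer has its use. The feasibility figures rest on an assumed base rate and on an unknown number of movers among the 100, and they need a reading under which a changed patient fills an enrolment place. The plan's forecast of those places counts none. The Cohort 2 rate and the AML subgroup rates are descriptive and carry no decision rule.

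A sensitivity analysis that added all movers to Cohort 1, and scored those without an adequate relapse profile as having no alteration, would not improve matters. Submission at relapse is optional, so it would mix non-submission with technical failure and pull the rate down.

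**Conclusion.** This is a gap that analysts would fill sensibly, and no change to the plan is needed. Counting by cohort at enrolment and on the initial sample is the reading that fits the enrolment wording, the accrual forecast and the stated use of later samples. On that reading the bias from movers is zero, the 67 newly diagnosed AML patients stay in their denominator, and the feasibility rule is unaffected. Technical failures already count in the denominator, because the rate is defined over enrolled patients.

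The shift of 1.5 to 7.5 points in the Cohort 2 rate arises only on the less natural reading. It also depends on an assumed 10% to 50% relapsing and on assumed rates of 25% and 10%, and its sign cannot be told from the documents. The loss of precision begins at 12 movers against a loose bound and a worst-case rate. A line in Section 12.4.1 confirming the enrolment basis would do no harm, but it would only record what the text already implies.
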